**Table 11-2 Schedule of Assessments for Patients with Suspicious ADE Occurrence (Unscheduled Visits)**

Evaluation	Suspicious ADE Assessment				
	Day of occurrence 	Day 2	Day 3	Day 5	Day 7 
Nasopharyngeal swab					
• RT-PCR (local) 				(X)	
• Viral shedding (central, qPCR and Cell culture)	X	X	X	X	X
• Genotyping of SARS-CoV-2 viral isolates (central) 				(X)	
Patient diary for SARS-CoV-2 Infection Symptom Checklist 				X	
SARS-CoV-2 infection related signs & symptoms assessment 	X	X	X	X	X
Vital Signs 	X	X	X	X	X
12-lead ECG 	X		X		X
Troponin test (I or T, only one applicable)	X		X		X

Abbreviations: ADE=antibody-dependent enhancement; ECG=electrocardiogram; qPCR= quantitative polymerase chain reaction; RT-PCR= reverse-transcription polymerase chain reaction; SARS-CoV-2=severe acute respiratory syndrome coronavirus 2; SpO2= peripheral capillary oxygen saturation

**Note:** For suspicious ADE assessment, patients can be hospitalized based on the investigator's decision. If required, additional assessments can be performed by investigator's discretion during the hospitalization period. Otherwise, the assessment will be done by out-patient visit. The genotype assessment marked as (X) will be performed in selected visits under the conditions explained in the relevant document of virology analysis.

1. The day of suspicious ADE occurrence.
  - If a patient has excessive progression of symptoms regarded as related to viral infection (e.g., excessive infiltration of inflammatory cells in the lung), OR
  - If a patient has other SARS-CoV-2 infection related signs and symptoms which are judged as possible manifestations of ADE according to the medical opinion of the Investigator.
2. If symptoms have not resolved or have worsened up to Day 7 after the day of suspicious ADE occurrence, same procedure will repeat until when the symptoms are resolved and/or no SARS-CoV-2 infection is confirmed by RT-PCR (local).
3. If required, RT-PCR (local) can be performed at any time by Investigator's discretion.
4. The genotyping will be performed on samples at time point when resistance is suspected, but not limited to.
5. For patients with suspicious ADE occurrence, patient will record the patient diary for SARS-CoV-2 Infection Symptom Checklist for 7 days from the day of suspicious ADE occurrence. Patients will be instructed to complete the diary twice a day at approximately 12-hour intervals in the morning (between 6 and 10 AM, approximately) and in the evening (between 6 and 10 PM, approximately).
6. The Investigator or designee will perform a respiratory signs and symptoms assessment (which should include, at a minimum, the examination of ear, nose, throat, sinuses, and lungs) and assessment for potential complications of SARS-CoV-2 infection.
7. Blood pressure, heart rate, respiratory rate, SpO2 and body temperature will be measured after the patient has rested quietly for at least 5 minutes. SpO2 will be measured while breathing normal room air. Temperature will be measured using tympanic thermometer throughout the study.
8. All scheduled 12-lead ECGs must be performed after the patient has rested quietly for at least 5 minutes. Regardless of the 12-lead ECG result, further cardiological evaluation can be performed at the Investigator's discretion.

## 11.2 SARS-CoV-2 Infection SYMPTOM CHECKLIST

All patients will complete the checklist twice a day at approximately 12-hour intervals in the morning (between 6 and 10 AM) and in the evening (between 6 and 10 PM) from Day 1 until clinical recovery or Day 28, whichever comes first.

After Day 28, additional recording of the diary will be required if following conditions are met (specified in [Section 6.3.1](#)):

- For patients who will achieve clinical recovery at Day 28, patients will record the diary until Day 29 to confirm whether it is maintained at least 24 hours.
- For patients who will show deterioration (at the discretion of the Investigator) after the achievement of clinical recovery, patient will record the diary until secondary achievement of clinical recovery.
- After Day 28 of regular scheduled study visit, for patients with suspicious ADE occurrence, patient will record the diary for 7 days from the day of suspicious ADE occurrence (specified in [Table 11-2](#)).

**Please read the below question and check one box that describes your symptoms of the following SARS-CoV-2 infection symptoms.**

		Absent (0)	Mild (1)	Moderate (2)	Severe (3)
1	Feeling feverish				
2	Cough				
3	Shortness of breath or difficulty breathing				
4	Sore throat				
5	Body pain or muscle pain				
6	Fatigue				
7	Headache				

Mild: no interference with normal daily activity

Moderate: interferes with normal daily activity

Severe: prevents normal daily activity

Source: [National Institute of Allergy and Infectious Diseases. Adaptive platform treatment trial for outpatients with COVID-19. 31 May 2020.](#)

12.11.	Antibody-dependent Enhancement.....	29
13.	CHANGES IN THE PLANNED ANALYSIS	29
13.1.	Changes in the Protocol	29
14.	REFERENCE LIST	30
15.	APPENDIX.....	31
	Appendix 1: Schedule of Assessments	31
	Appendix 2: Schedule of Assessments for Patients with Suspicious ADE Occurrence (Unscheduled Visits).....	35
	Appendix 3: SARS-CoV-2 Infection SYMPTOM CHECKLIST	36
	Appendix 4: CTCAE v5.0 for Clinical Laboratory Test Results.....	37
	Appendix 5: Tables, Listings and Figures in the Initial Analysis (For first CSR).....	40

LIST OF ABBREVIATIONS

Abbreviation	Definition
%AUC _{ext}	Percentage of the area extrapolated
ADA	Anti-Drug Antibody
ADE	Antibody Dependent Enhancement
AESI(s)	Adverse Event(s) of Special Interest
AE	Adverse Event
ATC	Anatomical Therapeutic Chemical
AUC _{0-inf}	Area under the Concentration-Time Curve from Time zero to Infinity
AUC _{0-last}	Area under the Serum Concentration-Time Curve from time zero to the Last Quantifiable Concentration
BLQ	Below the Lower limit of Quantification
BMI	Body Mass Index
CI	Confidence Interval
CL	Total Body Clearance
C _{max}	Maximum Observed Serum Concentration
CSR	Clinical Study Report
CTCAE	Common Terminology Criteria for Adverse Events
CV%	Percent Coefficient of Variation
DEC	Dose Escalation Committee
DRM	Date Review Meeting
DSMB	Data and Safety Monitoring Board
ECG	Electrocardiogram
eCRF	Electronic Case Report Form
EOT	End-of-treatment
GCP	Good Clinical Practice
HBsAg	Hepatitis B Surface Antigen
HBcAb	Hepatitis B Core Antibody
HIV	Human Immunodeficiency Virus
ICF	Informed Consent Form
ICH	International Council for Harmonisation
IRR	Infusion Related Reaction
ITT	Intent-to-treat
LLoQ	Lower Limit of Quantification
N/A	Not Applicable
NAb	Neutralizing Antibody
MedDRA	Medical Dictionary for Regulatory Activities
PK	Pharmacokinetic
PT	Preferred Term
qPCR	Quantitative Polymerase chain reaction
RT-PCR	Reverse Transcription Polymerase Chain Reaction

Abbreviation	Definition
SAE	Serious Adverse Event
SAP	Statistical Analysis Plan
SARS-CoV-2	Severe Acute Respiratory Syndrome Coronavirus 2
SD	Standard Deviation
SI	International System
SoC	Standard of Care
SOC	System Organ Class
$t_{1/2}$	Terminal Elimination Half-life
TEAE	Treatment-emergent Adverse Event
TEAESI	Treatment-emergent Adverse Events of Special Interest
TESAE	Treatment-emergent Serious Adverse Event
TLF	Table, Listing and Figure
T_{max}	Time to C_{max}
V_z	Volume of Distribution during the Terminal Phase
λ_z	Terminal Elimination Rate Constant
WHO	World Health Organization

1. ADMINISTRATIVE STRUCTURE

This study is being conducted under the sponsorship of CELLTRION, Inc. (hereinafter referred to as “CELLTRION”). The clinical monitoring, and pharmacokinetic (PK) parameter calculation are being performed under contract with [REDACTED] the PK and immunogenicity samples are being performed under contract with [REDACTED] and the virology samples is being performed under contract with [REDACTED] in collaboration with CELLTRION. The data management and statistical analyses are being performed by CELLTRION.

2. INTRODUCTION

This Statistical Analysis Plan (SAP) defines the statistical methods to be used by CELLTRION Clinical Statistics team in the analysis and presentation of data from CELLTRION study number CT-P59 1.2, entitled as “A Pilot Phase 1, Randomized, Double-blind, Placebo-controlled, Parallel Group, Single Ascending Dose Study to Evaluate the Safety, Tolerability and Virology of CT-P59 in Patient with Mild Symptoms of Severe Acute Respiratory Syndrome Coronavirus (SARS-CoV-2) Infection”.

There are two clinical study reports (CSRs) planned for the following time points:

- First CSR: The following data will be included, and list of TLFs is presented in [Appendix 5](#).
 - Virology (quantitative polymerase chain reaction [qPCR]) data up to Day 7 of each patient
 - PK and immunogenicity data up to Day 14 of each patient
 - Other safety data up to Day 14 of last enrolled patient
- Final CSR: All data after completion of the study.

If additional CSRs are required for regulatory or academic purposes, CSRs will be generated after the first database lock and unblinding process.

This SAP covers all specified analyses and is based on the following documents:

- Study Protocol Version 1.3 – 27th July 2020
- Study Protocol Version 1.3, including country specific A.2 – 02nd September 2020
- Unique Case Report Form Version 1.2 – 17th July 2020

Table, Listing and Figure (TLF) mock shells will be provided as an addendum to this document.

3. Study Objective

Primary and secondary objectives are described as below.

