## **2.2 Study Endpoints**

### **2.2.1 Primary Endpoints**

Primary endpoints will be analyzed based on the data up to Day 14 of the last enrolled patient.

- Treatment-emergent adverse events (TEAEs)
- Treatment-emergent serious AEs (TESAEs)
- Treatment-emergent AEs of special interest (TEAESI; infusion related reactions including hypersensitivity/anaphylactic reaction)
- Potential effects on the incidence of antibody-dependent enhancement (ADE)
- Vital signs (blood pressure, heart rate, body temperature, SpO2 and respiratory rate)
- Hypersensitivity monitoring
- Twelve-lead electrocardiogram (ECG)
- Severe Acute Respiratory Syndrome Coronavirus infection related signs and symptoms
- Radiography (chest x-ray and/or chest CT)
- Clinical laboratory test (clinical chemistry, hematology, and urinalysis)

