### **3.3 Dose Escalation and Stopping Criteria**

#### **3.3.1 Dose Escalation Criteria**

After each study drug administration, patients will be observed for 48 hours for evaluation of the safety and tolerability of the study drug. Despite the relatively long expected half-life of 18 days for CT-P59, the 48 hours of safety evaluation is justified given the expectation that any significant safety findings from the study drug administration should be apparent within post-48 hours considering the study drug is IV infusion.

When escalating dose from previous cohort to next cohort, Dose Escalation Committee (DEC) will review all available safety data of all patients in each cohort, within an observation period of 48 hours after study drug administration. If no safety or tolerability concern is observed, patients in next cohort will receive study drug.

Patients will be admitted for 72 hours post-study drug administration, and the duration of hospitalization may be extended at the discretion of the Investigator, so safety will be continuously monitored after the observation period of 48 hours.

If any safety concern including stopping rule specified in [Section 3.3.2](#) is raised, study can be temporarily stopped and the case will be immediate escalated to be reviewed at a DSMB meeting. The appointed independent DSMB members will evaluate the relationship to CT-P59 of the event with unblinded manner and review all available data and make a decision on continuation and the dose escalation of the study.

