## **4.4 Patient Withdrawal and Replacement**

Patients are free to withdraw from the study at any time for any reason. The Investigator may also discontinue the patient from the study at any time in the interest of patient safety.

If premature withdrawal occurs for any reason, the Investigator must determine the primary reason for a patient's premature withdrawal from the study and record this information in the patient's medical record and in the electronic case report form (eCRF). The primary reasons for premature withdrawal are as following:

- Withdrawal of consent
- Lost to follow-up
- Adverse event
- Death
- Investigator's decision
- Study termination by the Sponsor

For patients who are lost to follow-up (i.e., those patients whose status is unclear because they fail to appear for study visits without stating an intention to withdraw), the Investigator should show due diligence by documenting in the source documents steps taken to contact the patients, e.g., dates of telephone calls, registered letters, etc. Patients who fail to return for final assessments will be contacted by the center in an attempt to have them comply with the protocol. The status of patients who fail to complete final assessments will be documented in the eCRF.

When possible, the Sponsor should be notified of the withdrawal of a patient from the study. If necessary, the investigator may discuss with the Sponsor or its designee any patient's reason for withdrawal from the study. The Sponsor may be contacted if clarification is required on a case-by-case basis. All patients who are terminated from the study will retain their patient identification number.

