### **4.4.1 Recruitment of Additional Patients**

Generally, patients who receive study drug and discontinue before the study completion will not be replaced. However, if a patient who receives the study drug discontinues the study for a

reason other than patient's safety, the patient can be replaced upon decision of DEC. If a patient who is randomized but not receive study drug discontinues the study, the patient can be replaced.

Patients who failed Screening, for any reason, can be rescreened only once. If there is unusual situation so that additional rescreening should be considered, the Investigator is recommended to discuss with the Sponsor. Rescreened patient will be assigned with new patient identification number.

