**Table 6-3 Blood Sampling Time Points for Pharmacokinetic Assessment**

Day	Time point	Window
Day 1	Predose	Predose within the day + 15 minutes
	End of infusion	
	1 hour after end of infusion	
Day 2	24 hours after start of infusion	± 1 hour
Day 3	48 hours after start of infusion	
Day 5	96 hours after start of infusion	± 4 hours
Day 7	144 hours after start of infusion	
Day 10	216 hours after start of infusion	
Day 14	312 hours after start of infusion	± 1 day
Day 28	648 hours after start of infusion	± 3 days

Day 56	1,320 hours after start of infusion	$\pm 5$ days
Day 90/EOT visit	2,136 hours after start of infusion	

If the blood sample is unable to be analyzed or is missing at certain time point, some blood samples collected for immunogenicity assessment at same time point can be used for PK assessment. Analysis will be performed at the central laboratory.

Instructions for the blood collection, storage, and shipment to the central laboratory are described in [Section 6.5](#) and [Section 6.6](#).

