5. GENERAL STATISTICAL CONSIDERATIONS

Continuous data will be summarized using descriptive statistics: number of patients (n), mean, standard deviation (SD), minimum, median and maximum, unless otherwise specified. The descriptive statistics will be calculated using raw data before rounding although rounded values are listed. The following rules will be followed with regards to the number of decimal places:

- Minimum and maximum will be presented to the same number of decimal places in the source listing.
- Mean, median, geometric mean and percent coefficient of variation (CV%) will be rounded to one more decimal place than the maximum decimal place of values in the source listing.
- Standard deviation (SD) will be rounded to one more decimal place than mean.
- Only for PK section, point estimate and confidence intervals (CI) obtained from statistical procedures will be displayed to three decimal places. Also, standard error (SE) obtained from statistical procedures will be displayed to four decimal places.
- Kaplan-Meier estimates and days calculated using data/time will be displayed to two decimal places.

Geometric mean will not be reported if the dataset includes zero values and CV% will not be reported if the mean is zero.

Categorical data will be summarized using frequency tables showing numbers and percentages of patients. Percentages will be rounded to one decimal place and will be suppressed when the count is zero. The denominator for all percentages will be the number of patients within each treatment group for the set of interest, unless otherwise specified. Treatment group is defined in [Section 5.4](#).

Unscheduled visit will not be summarized in visit-based tables, unless otherwise specified. However, all data will be displayed in listings. Unless otherwise specified, listings will be sorted by the treatment group, patient number and visit, if applicable. In cases where more ordering is required, other variables will be included in the sort order as applicable.

When combining data from Electronic Case Report (eCRF) and analytical facilities such as Central Laboratory for PK, virology or immunogenicity, discrepancy will be handled as following:

- 1) Recorded as sample collected in eCRF but no corresponding results from analytical facility – listing will display only sample collection visit/date from eCRF;

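### At the first-CSR cut, TEAE, TESAE and suspicious-ADE percentages by dose rest on unequal follow-up that no table shows; a per-patient Day 14 window and a follow-up row would fix this cheaply

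*SAP*

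**What the plan says.** SAP section 2 gives different cuts for different data in the first CSR. qPCR stops at Day 7 of each patient, and PK and immunogenicity stop at Day 14 of each patient. The remaining safety data follow a calendar rule: "Other safety data up to Day 14 of last enrolled patient". This agrees with Protocol 2.2.1: "Primary endpoints will be analyzed based on the data up to Day 14 of the last enrolled patient".

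Dosing is sequential (Protocol 3.3.1 and 5.2: 20, then 40, then 80 mg/kg). Before each step the Dose Escalation Committee (DEC) must "review all available safety data of all patients in each cohort, within an observation period of 48 hours after study drug administration".

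SAP 12.1 defines a TEAE by onset after dosing, with no upper day limit. SAP 12.1.1, 12.1.2 and 12.11 summarise TEAEs, TESAEs and suspicious ADE as patient counts and percentages by treatment group. SAP section 5 sets the divisor: "The denominator for all percentages will be the number of patients within each treatment group". SAP 5.4 pools placebo across cohorts. SAP section 6 describes time on study only for patients who discontinue or end participation.

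SAP section 2 points to Appendix 5 for the first-CSR outputs.

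**The concern.** The first CSR reports the primary objective, and its adverse-event tables stand side by side by dose. With one calendar cut and cohorts dosed in order, the lowest dose is normally watched longest. A patient whose first event starts after their own Day 14 is more likely to be counted at 20 mg/kg than at 80 mg/kg. If the true risk does not depend on dose, the table then tends to flatter the highest dose, and the table itself gives no sign of it. Infusion-related reactions and by-visit summaries are little affected, because they are tied to the infusion or to a fixed visit.

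Secondarily, a reader who takes Protocol 2.2.1 at its word would expect each primary endpoint to be summarised on this cut.

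**Working it through.** **Planning figure.** The documents give no follow-up length by cohort at the cut. The only planning figure is the sample size: 3 cohorts x (5 + 1) = 18, that is 15 active and 3 placebo. It reproduces.

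**Follow-up floor.**
- Each step needs 48-hour data on every patient of the cohort before. Two steps give 2 x 48 h = 96 h = 4 days between any 20 mg/kg dosing and any 80 mg/kg dosing.
- Protocol Table 6-3 places Day 14 at "312 hours after start of infusion", and 312 / 24 = 13 days from dosing.
- With no enrolment time, withdrawal or replacement, follow-up is 17 / 15 / 13 days at 20 / 40 / 80 mg/kg. Pooled placebo averages (17 + 15 + 13) / 3 = 15 days.

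**Effect on the percentages.** Assume the same true Day 14 risk p at every dose.

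Constant hazard: risk at T days = 1 - (1 - p)^(T/13).

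| p | 20 mg/kg (17 d) | 40 mg/kg (15 d) | 80 mg/kg (13 d) | Placebo (mean of the three) |
|---|---|---|---|---|
| 20% | 25.3% | 22.7% | 20.0% | 22.7% |
| 30% | 37.3% | 33.7% | 30.0% | 33.7% |

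In expected patients out of 5, 20 versus 80 mg/kg: 1.27 versus 1.00 (difference 0.27) and 1.86 versus 1.50 (difference 0.36).

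Half of the Day 14 hazard in the first 48 h: with H = -ln(1 - p), risk at 17 days = 1 - exp(-(0.5H + 0.5H x 15/11)). This gives 23.2% versus 20.0%, and 34.4% versus 30.0%.

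No first event after a patient's own Day 14: no difference.

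**How often the count would change at the floor.** Under constant hazard, a 20 mg/kg patient has a first event in the extra 4 days with probability 0.253 - 0.200 = 0.053 (p = 20%) or 0.373 - 0.300 = 0.073 (p = 30%). The chance that none of five does is (1 - 0.053)^5 = 0.76 or (1 - 0.073)^5 = 0.69.

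**Exceptions.** Protocol 4.4 says "Patients are free to withdraw from the study at any time for any reason". Protocol 4.4.1 adds that, after a discontinuation for a non-safety reason, "the patient can be replaced upon decision of DEC". Example: one 20 mg/kg patient leaves 2 days after dosing and is replaced on the day cohort 3 is dosed. Mean follow-up at 20 mg/kg becomes (4 x 17 + 2 + 13) / 6 = 13.8 days, and the 20% risk shows as 20.8% versus 20.0%.

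**Primary endpoints against Appendix 5.** Protocol 2.2.1 lists ten.
- With a summary table, 4: TEAE (14.3.1.1), TESAE (14.3.1.2), TEAESI (14.3.1.4 and 14.3.1.5), suspicious ADE (14.3.6.10).
- With listings only, 6: vital signs, hypersensitivity monitoring, ECG, infection-related signs and symptoms, radiography, laboratory tests.
- For comparison, six tables serve secondary endpoints: 14.2.1.1, 14.2.1.7, 14.2.3.1 to 14.2.3.3, and 14.3.6.7.

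**The case against.** The case against is strong on several counts.

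- **The cut is the protocol's own rule.** A reader might infer that the SAP contradicts the protocol or mis-set the cut. It does not; the two agree.
- **The information exists.** The AE listing carries Time to Occurrence, and the study drug administration listing shows the dosing record, so follow-up can be worked out. A reader might infer from the Yes/No ADE listing that ADE onset is lost. But SAP 12.11 also sends the additional evaluations to their own listings, and Protocol Table 11-2 starts those visits on "The day of suspicious ADE occurrence". What is missing is a summary, not the data.
- **The size is small at the only figure the documents support.** No between-dose safety test is planned, and the exact 95% interval for 1 of 5 runs from 0.5% to 71.6%. Protocol 3.3.1 expects significant safety findings to be evident within 48 hours, which points to the smaller scenarios.
- **Larger distortions are tempting but unsupported.** If each cohort took 3 or 7 days to fill, a constant hazard would turn a 20% risk into 34.3% versus 22.0%, or 44.6% versus 24.6%. Those enrolment times appear nowhere in the documents. Nor is constant hazard an upper bound, since a rising hazard would exceed it.
- **The six listed-only endpoints are not hidden.** A reader might infer that they were quietly dropped. SAP section 2 openly makes Appendix 5 the first-CSR list, and SAP 12.2 openly defers laboratory summaries to the final CSR. Protocol 6.1.1.1 turns clinically significant abnormal results into AEs, so these already reach the TEAE tables.

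What survives is that the by-dose percentages are not on a common footing and that the tables do not say so.

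**Conclusion.** This is a cheap improvement to a descriptive report, not an error in the plan. Absent withdrawal or late replacement, the first-CSR percentages for TEAE, TESAE and suspicious ADE compare 20 mg/kg patients with at least about 4 days more follow-up than 80 mg/kg patients. The resulting difference at that floor is below one patient in five: 5.3 points at a 20% risk under constant hazard, 3.2 points if half of the hazard is front-loaded, and zero if no first event is late. The equal-risk assumption and both hazard shapes are illustrations, not document figures. The direction is not guaranteed, because replacement can nearly remove the gap.

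The consequence is limited in time. Dose escalation does not use these tables, and the final CSR, with AEs collected to Day 90, largely equalises follow-up.

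The missing tables for 6 of 10 primary endpoints are a secondary reporting gap against Protocol 2.2.1.

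**What to change.** Keep the protocol-defined cut and the all-data tables. In SAP 12.1, 12.11 and Appendix 5:

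1. Add TEAE, TESAE and suspicious-ADE tables limited to onset up to each patient's own Day 14. For TEAE and TESAE use the derived Time to Occurrence <= 14; it counts the dosing date as 1, so 14 is Day 14. For suspicious ADE use the date of the first visit in the suspicious-ADE schedule, because the eCRF item is Yes/No.
2. Show median, minimum and maximum days of follow-up per group for all dosed patients. This also exposes any withdrawal or replacement.

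As an option, add to Appendix 5 the summaries through Day 14 already specified in SAP 12.3 to 12.5, 12.8 and 12.10. Add also the laboratory shift tables in 12.2 (normal, abnormal not clinically significant, abnormal clinically significant), which need no SI conversion.

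The cost is a few extra runs of programs that the final CSR needs anyway, plus one derived ADE onset date. No new data are needed. The first CSR grows slightly, and the two sets of AE tables need clear labels. SAP section 5 allows an update before hard lock, so this can be settled before the code is broken.
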